With additional funding the study will include a patient follow-up 12 months after recruitment. Patients will be contacted by phone and asked to complete the WHO Quality Of Life BREF HIV tool (WHOQOL-BREF HIV⁴), those on ARVs will be given the ACTG ARV adherence tool while all participants will be asked to provide their feedback through an end-of-study questionnaire. The end of study questionnaire includes questions regarding their experiences during the study, their health status, their experience of HIV care, actual and opportunity costs, as well as a follow-up HIV/CD4 count knowledge questionnaire (tools can be found in appendix II). All responses will be recorded into REDCap on a mobile device by research staff.

Cost-Effectiveness analysis

A cost-effectiveness analysis will be conducted and compare the intervention arm with the standard of care arm from the societal perspective. Financial and economic costs will be assessed, which include ART costs, incremental health systems costs, and patient productivity loss due to morbidity and mortality. A potential for cost savings due to a reduction in low CD4 count results, Adverse Event (AE) and Opportunistic Infection (OI) will also be incorporated into the cost-effectiveness analysis.

Populations under consideration:

- General population
- General population categorised by 5 year age groups
- Specific populations: 18 to 25, over 25, men

Epidemiology outcomes:

- HIV mortality by 5 year age groups
- HIV incidence by 5 year age groups

⁴ The WHOQOL-BREF HIV is a cross-cultural quality of life assessment tool based on the WHO-QOL100 and the WHO-QOL-BREF. The WHO-QOL-BREF HIV measures quality of life for those with HIV over 31 questions.

- HIV prevalence by 5 year age groups
- Rate of progression to death through four equal durations
- HIV stages defined by mean CD4 count

Economic outcomes (to be obtained through the patient chart review include):

- ARV drug costs
- Treatment literacy level
- Clinic consultations (for ART delivery and OI and AE treatment)
- Laboratory tests (including CD4, viral load and routine monitoring tests)
- X-rays
- Diagnostic procedures
- Personnel training costs
- Number of consultations with i) doctors; ii) nurses consultations; iii) other health care personnel
- Number of home visits
- Number of counsellor consultations

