- Total annual per patient cost of providing a comprehensive model of ART linkage to care using the smartphone app (receiving laboratory results and linkage-to-care) plus cost over 10 years

Cost-effectiveness analysis involves the comparison of two or more competing methods in terms of both their costs and consequences. The outcome measure of the cost-effectiveness work will be the cost of ART initiation with a particular intervention in South African Rand (ZAR) per disability adjusted life year (DALY) averted. The lower the cost per DALY averted, the more cost-effective the intervention. It will be based on a 5% discount rate.

For each target and cost scenario, this analysis will be able to provide the estimated impact in terms of OI and AE averted, impact in HIV stage defined by CD4 count and treatment costs and deaths averted due to ART linkage to care of those using the smartphone app.

Participant opt-out

All participants will be provided with contact information for the study team and will be informed that they can drop out of the study at any time with no consequences (as per Good Clinical Practice guidelines). Should a participant request to withdraw from the study the team will identify their informed consent sheet and mark it accordingly, remove the patient's data from REDCap and notify the NHLS if they are part of the intervention arm to ensure they will not receive additional notifications of laboratory results. The participant will be asked if they would like to keep their username and password active to access the app in the future; their account will be deleted or kept accordingly.

Safety considerations

Accidental disclosure (through phone loss/theft/borrowing or any other method) will be limited by the study team as much as possible. This will be done actively by having a username, password AND PIN code for app use. Additionally, the recruitment team will inform participants of the sensitive information on the app and request that they don't share it with

anyone. Lastly, the app icon and name will not relate to health or HIV in any way; only after the username and password is entered will health-related terminology be used.

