From the opportunity cost data collected from patients we will analyse clients' time spent travelling to and being at health facilities to assess service uptake to measure actual patient opportunity cost. The team will separate costs of implementing the SmartLtC intervention and standard of care into categories (e.g. ART, other medicine, laboratory & other tests, health personnel time, overhead and capital costs, patient transport, and lost patient time) which will come from the WHO CHOICE database. Additionally, we will calculate DALY's saved based on disability and deaths averted due to the intervention with weights based on the 2010 Global Burden of Disease Study.

Regulatory compliance

The following methods will be employed to ensure high quality assurance throughout the study period:

- All study staff are GCP trained and certified throughout the study period.
- The study will not start before it receives ethics permission from the University of Witwatersrand Human Research Ethics Committee (Medical) and approval from the district research committee.
- All data collected for the study will be treated sensitively and stored in a secure location (for paper documents) or a secured, password and encrypted database (for electronic records)

Ethics

As a research institute, all RHI research projects go through both internal and external research review. The external review is done through the University of Witwatersrand's ethics board, the Human Subjects Research Committee (HSRC). The SmartLtC study will not start recruiting patients before the committee has reviewed the study and has provided ethics clearance.

Informed consent forms

Informed consent form can be found at the end of this document in Appendix I.

Expected outcomes

This study is expected to have the following outcomes by the end of the project:

- An analysis of the effect of the app in linkage to care for the study population and in different demographic and socioeconomic subgroups
- An understanding of the acceptability of the laboratory result app
- Incremental cost-effectiveness ratio for SmartLTC compared to SOC from the societal perspective and the DOH perspective
- One or more conference presentations on the study and outcomes
- One or more published academic journal articles describing the study and outcomes
- A study report providing recommendations to policy makers, other study teams, and health practitioners.

Dissemination of results and publication policy

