3.2 Secondary objective/s

- 3.2.1. To compare ART initiation rates between intervention and control arms.
- 3.2.2. To assess the feasibility and acceptability of receiving laboratory results to a personal smartphone.
- 3.2.3. To assess secondary effects from improved patient information, including return rates after falling out of care (assessed through routine patient record reviews), patient satisfaction (through face-to-face surveys at the 6-month follow-up visit and end of the study), and rates of additional blood tests (especially CD4 count, viral load).
- 3.2.4. To assess patient knowledge levels of their laboratory results.
- 3.2.5. To specifically look at 2 subgroups – men and young adults (18 to 25 years of age), who would particularly benefit from improved linkage to care.
- 3.2.6. To assess the performance of the app in clients with different levels of education and standard of living, and see if there are differences in clinical and usage outcomes
- 3.2.7. To evaluate differences in linkage-to-care, HIV-knowledge, adherence to medication (treatment patients only) and reported quality of life between wellness and treatment patients.
- 3.2.8. To assess the financial and economic costs of providing the SmartLtC smartphone app.
- 3.2.9. To determine the incremental cost, and cost-effectiveness of ART initiation link to the smartphone app (receiving laboratory results and linkage-to-care) as compared to the standard ART initiation.

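### The rule that a lower cost per DALY averted is better holds only when the app costs more and averts DALYs; outside that case it can misread the result

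*Protocol*

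**What the plan says.** The Protocol's Cost-Effectiveness analysis section defines the outcome measure as "the cost of ART initiation with a particular intervention in South African Rand (ZAR) per disability adjusted life year (DALY) averted" and then gives the only reading rule in either document: "The lower the cost per DALY averted, the more cost-effective the intervention". The rule carries no condition on the sign of the cost or of the effect.

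The ratio is incremental. Expected outcomes promises an "Incremental cost-effectiveness ratio for SmartLTC compared to SOC from the societal perspective and the DOH perspective", and SAP 3.2.9 (the same as Protocol secondary objective 9) is "To determine the incremental cost, and cost-effectiveness of ART initiation link to the smartphone app".

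The Cost-Effectiveness analysis section also allows for savings on the cost side ("A potential for cost savings due to a reduction in low CD4 count results", together with fewer adverse events and opportunistic infections). It lists age and sex groups as populations to be considered: 5-year age bands, 18 to 25, over 25, and men.

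The same section counts "patient productivity loss due to morbidity and mortality" among the costs. For the effect side, the Protocol's Analysis plan says "we will calculate DALY's saved based on disability and deaths averted due to the intervention".

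Neither document gives a dominance rule, a net-benefit measure, a willingness-to-pay threshold or an interval for the ratio. The SAP restates the economic objectives (3.2.8, 3.2.9), and its section 7 tables contain nothing economic.

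**The concern.** A ratio of two differences can be ordered from low to high only while both differences are positive. Once either is negative, one value can describe opposite results. A negative ratio can mean that the app is cheaper and better, or that it is dearer and worse. Read literally, the stated rule favours both, and may favour the second more.

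At stake is the conclusion on secondary objective 9, which feeds the recommendations to policy makers listed under Expected outcomes. The primary linkage comparison is not affected.

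**Working it through.** The documents state no incremental cost, DALY total, threshold or ratio, so there is no figure to reproduce. The check is algebra with assumed inputs, followed by a calculation of how often the problem region would be reached.

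**1. Does the rule order results correctly?**

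Let ΔC be incremental cost and ΔE be DALYs averted, both app minus standard of care. The ratio is ΔC/ΔE. Net monetary benefit is L × ΔE − ΔC, where L is the threshold in rand per DALY. The per-patient values and thresholds below are assumptions chosen for illustration.

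| Result | ΔC (R) | ΔE | Ratio (R per DALY) | Net benefit at L = 0 / 10,000 / 50,000 |
|---|---|---|---|---|
| A: dearer, better | +500 | +0.05 | +10,000 | −500 / 0 / +2,000 |
| B: cheaper, better | −500 | +0.05 | −10,000 | +500 / +1,000 / +3,000 |
| C: cheaper, twice the benefit of B | −500 | +0.10 | −5,000 | +500 / +1,500 / +5,500 |
| D: dearer, worse | +500 | −0.05 | −10,000 | −500 / −1,000 / −3,000 |
| E: dearer, slightly worse | +500 | −0.005 | −100,000 | −500 / −550 / −750 |
| F: cheaper, worse | −500 | −0.05 | +10,000 | +500 / 0 / −2,000 |
| G: dearer, no effect | +500 | 0 | undefined | −500 / −500 / −500 |

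- B and D have the same ratio, although B dominates standard of care and D is dominated by it.
- E has the lowest ratio, so the rule puts a dominated app first.
- C is better than B at the same saving, yet its ratio is higher, so the rule puts C behind B.
- A and F have the same positive ratio and opposite meanings.
- Net benefit at R50,000 orders the results C, B, A, G, E, F, D, as it should.

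**2. How often would the effect estimate have the wrong sign?**

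Inputs:
- Control linkage of 52.5%, the midpoint of the 50-55% in the Protocol's Population section.
- About 350 participants (SAP section 5), taken as n = 175 per arm. The 1:1 split is an assumption, as no ratio is stated.
- DALYs averted taken to have the sign of the linkage difference (assumption).

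With p = 0.525 and true gain d, the standard error is √[p(1−p)/n + (p+d)(1−p−d)/n], and P(wrong sign) = Φ(−d/SE).

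- d = 0: 50%, at any n.
- d = 0.05: SE = √[(0.2494 + 0.2444)/175] = 0.0531; Φ(−0.94) = 17%.
- d = 0.10: SE = √[(0.2494 + 0.2344)/175] = 0.0526; Φ(−1.90) = 3%.
- d = 0.20 (the design difference, read as percentage points): SE = √[(0.2494 + 0.1994)/175] = 0.0506; Φ(−3.95) is about 0.
- Subgroup with an assumed 50 per arm, d = 0.05: SE = √[(0.2494 + 0.2444)/50] = 0.0994; Φ(−0.50) = 31%.

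As a cross-check on deaths instead of linkage, take 175 per arm and equal assumed death risks of 2% to 10%. The app arm then has more deaths in 42% to 46% of trials (exact binomial).

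**3. What does counting illness and death on both sides do?**

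Suppose productivity worth g rand is credited for each DALY averted. The ratio becomes (ΔC − gΔE)/ΔE = ΔC/ΔE − g, a constant shift.

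- Result A moves from +10,000 to 0 at g = 10,000 and to −10,000 at g = 20,000.
- Result D moves from −10,000 to −20,000 and −30,000.

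The order of results does not change. A working app looks cheaper per DALY, and negative ratios become more common.

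**The case against.** The best defence is that the sentence explains what a cost-effectiveness ratio is and is not a decision procedure. It sits beside a textbook description of the method, and no ranking or adoption decision is tied to it. Under Potential risks, roll-out depends on improved linkage, and an app with observed linkage below control would fail that test. The section also promises deaths and opportunistic infections averted, so a competent analyst should see the direction of effect. This limits the practical harm, but it does not make the rule correct. It is the only reading rule given, and nothing in either document qualifies it.

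The defence is also right that the 50% figure under no effect says nothing about this sample size, and that at the design difference the risk is about zero.

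A reader might infer several stronger points, which the documents do not support:

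- *Double counting causes the misranking.* It does not. The sign of the ratio is enough, and under proportional valuation the double count shifts every ratio equally. A non-proportional valuation could change the order, but the documents give nothing to size that.
- *An app with no effect would rank as best.* At exactly zero effect the ratio is undefined. Just above zero it is very large (R500/0.0001 = R5,000,000 per DALY) and ranks last. The false top rank needs an estimated loss of DALYs.
- *The plan confuses average with incremental ratios.* The outcome wording could be read per arm, but objective 9, SAP 3.2.9, the arm comparison in the Cost-Effectiveness analysis section and Expected outcomes together settle it as incremental.
- *Productivity loss must leave the societal base case.* That depends on a costing convention the documents do not state. Expected outcomes also promises a health-department perspective, which may well omit it, although its cost items are not listed.

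**Conclusion.** The concern holds in limited form. The rule is valid only when the app costs more and averts DALYs. It reads a dearer, worse app as favourable, possibly as best, and among cost-saving results it can prefer less benefit. The algebra needs no assumption about the trial.

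How often this would matter does rest on assumptions: 175 per arm, 52.5% control linkage, and DALYs following linkage. On those, a wrong-sign effect is estimated in about 17% of trials at a true gain of 5 points, 3% at 10 points and about 0 at 20 points. It is more likely in the small age and sex groups. The misreading of a dominated app also requires that the app adds cost. The second failure needs a net saving; the plan allows for savings but does not predict one.

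The overlap between productivity loss and DALYs is a separate and lesser matter. It lowers the reported ratio of a working app by an amount the documents do not allow one to estimate. It is an unstated convention and not a demonstrated error.

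This touches one secondary objective. It is worth correcting because the economic result is meant to inform policy and the correction is cheap.

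**What to change.** In the Protocol's Cost-Effectiveness analysis section, replace the reading rule with the following, and carry it into the SAP:

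- Report incremental cost and incremental DALYs averted (app minus standard of care) separately, each with a bootstrap 95% confidence interval.
- Where the two signs differ, state which arm dominates.
- Base the conclusion on incremental net monetary benefit, L × ΔE − ΔC, over a stated range of thresholds.
- Quote the ratio only where the app costs more and is more effective. Apply the same rule to the age and sex groups.
- State whether productivity loss from morbidity and mortality is in the societal numerator, and show the result with and without it.

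The cost is some wording and a little more analysis code, with no new data. The result without productivity loss may look less favourable to the app.

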If interest is shown, the study recruiter will first inquire about their age and pregnancy status as the study only allows those who are 18 years of age and older and not currently pregnant. Upon finding individuals who are under 18 or are pregnant the recruiter will inform them they are not eligible, thank them for their time, and record the reason for non-participation in the study database. For individuals who are 18 or older and are not pregnant, the recruiter will invite them to a private space where they will be asked (non-identifying) demographic and socioeconomic questions. The demographic and socioeconomic questions asked to all potential participants will allow the study team to perform a comparison later to determine what differences there are between smartphone owners and non-owners, and how generalisable the results are. Following the demographic and socioeconomic questions will be a number of inclusion and exclusion criteria questions to confirm the remaining eligibility criteria (smartphone ownership, literacy, photo proof of identification, willingness to participate). If an individual is found to be ineligible the recruiter will inform them they are not eligible, thank them for their time, and record the reason for non-participation in the study database. If the reason for exclusion is that they do not own an Android phone with data, the type of phone will also be noted.

Patients who fit the study eligibility criteria will be invited to participate, provided a broad overview of the study, explained the randomisation, read the informed consent documentation, and asked to sign it after being told that participating requires them to allow the study team to monitor their laboratory results throughout the study and contact them with a follow-up questionnaire about their experiences of the study and HIV care they received. At any time, if an individual decides they do not want to participate, the recruiter will thank them for their time, and record the reason for non-participation in the study database.

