Upon signing informed consent, their personal details including name, surname, ID number, and a baseline survey which consists of a HIV/CD4 count knowledge questionnaire (all tools listed in appendix II) will be recorded into REDCap (Harris et al, 2009), an electronic data capture tool hosted at Wits University², using a tablet device by trained research staff. At the end of the recruitment process all patients will be provided their R50 participation allowance. Patients in both study arms will be encouraged to return to the clinic as per the clinic guidelines to receive their CD4 result and attend wellness or HIV care follow-up.

REDCap will randomise the participant to the standard of care or intervention arm through the device without informing the participant. Participants randomised to the standard of care arm will be provided with a copy of their signed informed consent document and thanked for their time.

Participants randomised to the intervention arm will be told about the smartphone app and told how it works. The study staff member will install the app on the participant's phone and assist the participant in setting up an account with a username, password and PIN number and provide an overview of how the app and notification system works. Participants will be

² REDCap (Research Electronic Data Capture) is a secure, web-based application designed to support data capture for research studies, providing: 1) an intuitive interface for validated data entry; 2) audit trails for tracking data manipulation and export procedures; 3) automated export procedures for seamless data downloads to common statistical packages; and 4) procedures for importing data from external sources.

informed that they are welcome to use the app at any time, and it will notify them when a laboratory result has arrived. As mentioned above, the cost per laboratory result received is approximately R0.02. Patients will be informed of this cost prior to participating.

[figure not shown]

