³ For example, if a CD4 count of 250 is returned, the number will be shown in red with an informative note explaining that that CD4 value is abnormally low and request that the patient attend to the clinic for further care as soon as possible. Alternatively, if the a CD4 count result of 700 is returned, the number will be shown in amber (a warning colour) with an informative note explaining that the CD4 count value is within the normal range and they should return to the clinic for wellness counselling and then have another CD4 count test in 6 months. For any result (CD4 or viral load) the patient will be able to get more information about HIV/AIDS, CD4 counts and viral loads within the app, see a list of frequently asked questions (FAQ), given clickable links to get external (web) information or provided contact numbers for the study team (for study or app-related questions) or the National HIV/AIDS helpline (for HIV-related questions).

Baseline recruitment will include questions on basic demographics. Throughout the study the team will monitor the number of times the app is accessed to view laboratory results and/or support information by the user; and loss-to- follow-up. Healthcare monitoring, measured by appropriate laboratory adherence to treatment guidelines, will be monitored through the NHLS database; in particular, we will monitor whether providing information to the patient to prompt the health care worker improves compliance with guidelines. All patients who exit from the trial will be given a survey that includes questions to assess CD4 count and HIV knowledge, health status, health care access, and patient satisfaction with the app, as well as with the health care services. This will allow us to compare how much the app has contributed to linkage to and retention in care, as well as to patient understanding of their health management.

After 8 months of participating in the study the research team will monitor participant attendance to a follow-up laboratory test through the NHLS test database. The patient will not be contacted at this point. Data will be analysed comparing the standard of care arm with the intervention arm.

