Should a participant have any issues regarding their diagnosis or the study they will be able to access help. At recruitment they will be told that for HIV-related queries they can call the HIV/AIDS helpline numbers that are shown in the app. For study-related queries, they can call the study team on the phone numbers that are listed in the study documentation.

Data management & statistical analysis

Data management

Patient recruitment, demographic, baseline and follow-up survey data will be collected by a trained and GCP certified researcher using a mobile device (tablet) connected to the REDCap database. REDCap is a secure web-based application designed for virtually collecting clinical research data and is used by over 150,000 projects around the world (more information at: <http://project-redcap.org/>). The REDCap Android app, which will be installed on the tablets, allows for off-line data collection if there is no internet connection available.

Laboratory results will be added to the NHLS laboratory database as they are received and pushed to the participant through an application layer that is part of the smartphone app. The REDCap database will be connected to the NHLS laboratory database using an API (application programming interface). All HIV-related NHLS laboratory results will be recorded as part of the study to monitor the total number and frequency of laboratory tests on study participants. All data transmission between electronic databases/servers will be secured and encrypted.

Paper records (completed informed consent) will be in the control of study staff for the day they are collected. At the end of each day they will be returned to a centralised location (e.g.: RHI offices) where they will be scanned and archived in a data storage room. Once archived the paper records will only be accessed under special circumstances (e.g.: a patient withdraws or a confirmation of a patient's acceptance to be in the study is required).

Data analysis will be conducted by research staff with all identifying participant data de-identified.

Analysis plan

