The primary outcome, linkage to care around 6 months after initial diagnosis, will be available after the final patient recruited has reached the 8 month mark, allowing immediate assessment of the feasibility and immediate impact of the app on initial linkage to care. Thereafter, retention in care, defined as continuation of HIV care (regular clinic visits with laboratory tests and/or medicine pickup) after the linkage to care visit will be assessed 12 months after linkage to care had been made.

Analysis will be done by the study team using STATA. Intention-to-treat will be the primary approach of the analysis and all missing data points will be considered to be loss-to-follow-up. Analysis of the primary outcome will be based on a chi-squared test comparing the proportion of individuals between the study arms and within study sites. A

logistic regression model, with linkage to care as the dependent variable, will be a secondary analysis of the primary outcome.

For secondary outcomes, chi-squared tests will be used for binary variables, Mann-Whitney-U tests for non-normally distributed variables, and t-tests for continuous variables. Relative risk calculations (at 95% confidence) will be used to compute binary variables. Survival analysis will be conducted to determine linkage outcomes at 6 months. A sensitivity analysis will be conducted using regression analysis to identify and adjust for potential confounders.

For the cost-effectiveness analysis, we will have data on direct costs and understand the resource requirements for the development of the app. We will corroborate our existing estimates of the smartphone data costs of the patient. The study team will collect data on clients' opportunity cost as part of the end of the study participant interview as linkage to care (as opposed to non-linkage to care) actually takes more time. We will use primary data collect through this study to calculate unit costs associated to providing HIV services.

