6.7 Methods for dealing with withdrawals, missing data, outliers

6.7.1. Withdrawals/opt-outs will be considered loss-to-follow-up

STATISTICAL ANALYSIS PLAN

SmartLtC: Does an Android Smartphone App Increase Linkage To Care in Johannesburg

[figure not shown]
- 6.7.2. As REDCap is used as the data collection tool, minimal missing data is expected. If missing data is found, the study team will contact the study participant by telephone.
- 6.7.3. Outliers will be identified using STATA and either removed or replaced with average values on a case-by-case basis.

STATISTICAL ANALYSIS PLAN

SmartLtC: Does an Android Smartphone App Increase Linkage To Care in Johannesburg

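### The opt-out rule removes withdrawn participants' data from REDCap, which does not fit the intention-to-treat primary analysis or SAP 6.7.1 and leaves the primary denominator undefined

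*Protocol*

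**What the plan says.** **What happens at withdrawal.** Under Participant opt-out, the protocol has the team mark the consent sheet and then "remove the patient's data from REDCap and notify the NHLS if they are part of the intervention arm".

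**What REDCap holds.** Under Recruitment, REDCap stores "their personal details including name, surname, ID number, and a baseline survey" and generates the allocation: "REDCap will randomise the participant to the standard of care or intervention arm through the device without informing the participant". Under Data management, "The REDCap database will be connected to the NHLS laboratory database using an API". The NHLS database is where attendance for the follow-up test is read.

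**What the analysis requires.** The protocol's Analysis plan states: "Intention-to-treat will be the primary approach of the analysis and all missing data points will be considered to be loss-to-follow-up". SAP 6.7.1 states: "Withdrawals/opt-outs will be considered loss-to-follow-up". The SAP names no analysis population. Neither document says outright whether a person lost to follow-up counts as not linked or is left out of the denominator.

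**What is foreseen.** Just before its Sample Size section, the protocol says it expects balance between arms unless controls ask to withdraw because they did not get the app. SAP 4.3.1 says there was no blinding.

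**The concern.** Intention-to-treat needs every randomised person to be counted in the assigned arm. SAP 6.7.1 needs the same thing: a person can be classed as lost to follow-up within an arm only if that person and the arm are still on record. The opt-out instruction, taken at its word, removes the record from the system that holds both. Nothing in either document says that a study ID, the arm or the withdrawal date is kept.

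This matters most if withdrawal differs between arms, and the protocol itself names a reason why it might. The one arm-specific step at withdrawal, notice to the NHLS, applies only to the intervention arm. The withdrawals the protocol foresees, those of controls, would therefore leave the weaker trace.

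What is at stake is which denominator the primary test uses. As written, the team could follow the opt-out text (deleted), or SAP 6.7.1 read as not linked, or SAP 6.7.1 read as excluded. That choice could be made after the data are known.

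**Working it through.** The plan gives no figure to reproduce here, so the check has two parts: the texts side by side, and an illustration of how far the rules can diverge.

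**Texts**

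| Source | Effect on a withdrawn participant |
|---|---|
| Protocol, Participant opt-out | Data removed from REDCap |
| Protocol, Analysis plan | Intention-to-treat, so kept in the assigned arm; missing data treated as loss to follow-up |
| SAP 6.7.1 | Loss to follow-up, not further defined |
| Protocol, Sample Size | 27% loss allowance, which could suggest exclusion from the analysed number |

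Kept and counted as not linked is the more natural reading of intention-to-treat for an attendance outcome. The 27% allowance leaves some doubt.

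**Illustration: inputs**

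- n = 175 per arm: half of the approximately 350 in SAP section 5. Equal allocation is an assumption.
- p = 0.525 linkage in both arms: the midpoint of the 50-55% in the protocol's Population section. No true effect.
- w = control-only withdrawals, assumed to be 4, 9 or 18 (about 2%, 5% and 10% of 175).
- q = the rate at which those w people would have linked, assumed to lie between 0.30 and 0.70.

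**Formulas**

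- Linkage among the remaining controls: r = (n·p − w·q)/(n − w).
- Deleted: apparent app-minus-control difference = p − r.
- Kept as not linked: apparent difference = p − (n − w)·r/n = w·q/n.
- Gap between the two rules = r·w/n.

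False-positive rates come from exact enumeration of two binomials with w fixed, using the pooled chi-squared test at 1.96. With no withdrawals the rate is 4.8%.

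**Results for w = 18**, with n·p = 175 × 0.525 = 91.875:

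| q | r | Deleted: shift | Deleted: false-positive rate | Not linked: shift | Not linked: false-positive rate | Gap |
|---|---|---|---|---|---|---|
| 0.30 | (91.875 − 5.4)/157 = 0.551 | −2.6 points | 7.6% | 5.4/175 = +3.1 points | 7.9% | 5.7 points |
| 0.525 | (91.875 − 9.45)/157 = 0.525 | 0 | 5.0% | 9.45/175 = +5.4 points | 16.1% | 5.4 points |
| 0.70 | (91.875 − 12.6)/157 = 0.505 | +2.0 points | 6.6% | 12.6/175 = +7.2 points | 25.9% | 5.2 points |

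**Fewer withdrawals.** At q = 0.525, counting them as not linked gives +1.2 points and 5.2% for w = 4, and +2.7 points and 7.3% for w = 9. Deletion gives no shift at that q. The gap between the rules is about 1.2 and 2.7 points respectively.

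**Outside the 30-70% range.** If the 18 would never have linked (q = 0), then r = 91.875/157 = 0.585. Deletion shifts the difference by 0.525 − 0.585 = −6.0 points, and counting them as not linked shifts it by nothing. Which rule does less harm therefore depends on q, which is unknown.

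**Milder imbalance.** With 9 app and 18 control withdrawals, all counted as not linked at q = 0.525, the shift is (18 − 9) × 0.525/175 = +2.7 points and the false-positive rate is 6.7%.

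**The case against.** The strongest reply is that deletion is not shown to be the harmful rule. The largest error rates above, 16.1% and 25.9%, arise when withdrawals are counted as not linked; deleting the same 18 people gives 5.0% to 7.6%. That stands. A reader might infer from the conflict that deletion seriously inflates the error rate of the primary test. The documents and the arithmetic do not support this. They show only that the rules give different answers.

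A second tempting inference is that the arm of a withdrawn person is lost for good and intention-to-treat becomes impossible. That is also too strong. Nothing says the allocation log is erased, and the data to be removed might mean only entered personal and survey data. The protocol archives the consent sheets and names withdrawal as a reason to retrieve one. Marked sheets could give total withdrawals, NHLS notices the intervention ones, and subtraction the controls. REDCap's audit trail, mentioned in a protocol footnote, may help as well. But consent is signed before allocation, so the sheet need not show the arm, and no text plans any such recovery.

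Third, withdrawal may be rare. Controls have little to opt out of: REDCap allocates without telling the participant, the 8-month outcome is read from the NHLS database ("The patient will not be contacted at this point"), and a person who simply stays away has not withdrawn. No withdrawal rate is given, and the case of 18 controls and no app users is deliberately extreme. All of this stands and limits the size.

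Finally, the consent form and the flowchart of SAP section 7.1 are not in this copy. The flowchart may already count withdrawals by arm, and removal may be a promise made to participants. Neither can be checked. SAP 6.7.1 does supply a rule, but it does not say what loss to follow-up means or how the rule applies to a removed record.

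**Conclusion.** The inconsistency is real and should be fixed. Read literally, the opt-out text removes randomised people from the primary denominator, while the protocol's Analysis plan and SAP 6.7.1 need them in it, and loss to follow-up is undefined. Loss of the arm is likely but not certain.

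The size cannot be derived from the documents. Under the stated assumptions, 18 control-only withdrawals separate the two rules by 5.2 to 5.7 points, against a design difference of 20%. With 4 they separate by about 1.2 points, which is negligible. With no true effect, there is no bias under either rule if withdrawal and withdrawers' linkage are the same in both arms. Neither rule is uniformly better. The case for change is that the rule should be written down in advance and be workable by arm. Confidence is medium, because the withdrawal rates, the consent terms and the flowchart are not available.

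**What to change.** **Protocol, Participant opt-out.** Reconcile it with the Analysis plan. Withdrawal stops study contact and notifications and removes identifying and survey data, but a de-identified study ID, arm, site, randomisation date and withdrawal date are kept. At withdrawal, ask whether the NHLS outcome may still be used. If the participant agrees, record it before identifiers are removed or keep the link until 8 months. Agreement is needed because the consent terms tie laboratory monitoring to taking part: "participating requires them to allow the study team to monitor their laboratory results throughout the study".

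**SAP 6.7.1.** State that:

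- all randomised participants stay in their arm's denominator;
- a permitted NHLS outcome is used first;
- remaining withdrawals count as not linked in both arms;
- withdrawals are reported by arm.

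**Sensitivity analyses.** Because counting control withdrawals as not linked can favour the app, add two: one excluding withdrawals, and one least favourable to the app (control withdrawals linked, app withdrawals not linked).

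**Records already removed.** The SAP describes randomisation in the past tense, so this may matter most. Recover counts by arm from consent sheets, NHLS notices and the audit trail, and state any that cannot be placed. If the consent form promised full deletion, honour it and do not call the analysis set full intention-to-treat.

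**Cost.** Wording changes in two documents, an ethics amendment and two short analyses. Some outcomes will stay unknown, and an allocation record is kept for people who withdrew.
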